- z On Days 0 and 231, patients in the PK/PD subgroup will have PK samples taken pre-dose (within 1 hour of planned dosing start; -5 minutes), EOI (+5 minutes), and 1, 2, 4, 6, and 24 hours postinfusion. In addition, a plasma PK sample will also be collected 3, 7, and 17 days (± 1 day) after dosing with ALN-TTR02 for the study visits noted. The windows for sampling are ± 5 minutes for the 1, 2, 4, and 6 hour sampling periods; and ± 120 minutes for the 24 hour sampling period.
- aa On Days 0 and 231, patients in the PK/PD subgroup will have a urine sample for PK analysis taken pre-dose (within 1 hour of planned dosing start; -5 minutes), EOI (+5 minutes), and 6 and 24 hours postinfusion. In addition, a urine PK sample will also be collected 3, 7, and 17 days (± 1 day) after dosing with ALN-TTR02 for the study visits noted. The windows for sampling are ± 5 minutes for the 1, 2, 4, and 6 hour sampling periods; and ± 120 minutes for the 24-hour sampling period.
- bb Adverse events are to be documented beginning with the initiation of the first infusion.

Table 1-2: Schedule of Assessments for Year 2 — ALN-TTR02 Administered Once Every 3 Weeks

Procedure	Visit Type	Dosing										Mid-year/ Annual Efficacy Assessment	21- and 56-day Follow-up ^a		Early Termination
		55 & 82	58 & 85	61 & 88	64 & 91	67 & 94	70 & 97	73 & 100	76 & 103	79 & 106	81 & 108		109	114	
	Study Day	D378 & D567	D399 & D588	D420 & D609	D441 & D630	D462 & D651	D483 & D672	D504 & D693	D525 & D714	D546 & D735	D560 & D749	D756	D791	N/A	
	Window	±3D	±5D	±5D	±5D	2D to 7D									
Physical Examination												X	X	X	
Weight ^b	X	X	X	X	X	X	X	X	X	X	X	X	X	X	
Vital Signs ^c	X	X	X	X	X	X	X	X	X	X	X	X	X	X	
12-lead ECG ^d												X	X	X	
Hematology ^e											X		X	X	
Serum Chemistry and Urinalysis ^e					X					X		X	X	X	
Thyroid Function Tests and Coagulation Studies ^e										X		X	X	X	
Ophthalmology Exam											X			X	
PD Assessments:															
TTR protein (ELISA and turbidimetric) ^f	X	X	X	X	X	X	X	X	X	X	X	X	X	X	
RBP and Vitamin A ^f					X					X	X	X	X	X	
Other Assessments:															
Exploratory Biomarkers ^g					X					X					
Anti-drug Antibodies										X ^h					
Pharmacoeconomics Questionnaire											X			X ⁱ	

Procedure	Visit Type											Mid-year/ Annual Efficacy Assess- ment	21- and 56-day Follow-up ^a		Early Termination
		55 & 82	58 & 85	61 & 88	64 & 91	67 & 94	70 & 97	73 & 100	76 & 103	79 & 106	81 & 108				

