5.5 Premedication Plan

Prior to ALN-TTR02, patients will receive the following premedications:

- Intravenous dexamethasone (10 mg) or equivalent, administered at least 60 minutes prior to the start of the infusion of ALN-TTR02;
- Oral paracetamol (500 mg) or equivalent at least 60 minutes prior to the start of the infusion of ALN-TTR02;
- Intravenous H2 blocker (e.g., ranitidine 50 mg, famotidine 20 mg, or equivalent other H2 blocker dose) at least 60 minutes prior to the start of the infusion of ALN-TTR02; and
- Intravenous H1 blocker: diphenhydramine 50 mg (or equivalent other IV H1 blocker available at the study site) at least 60 minutes prior to the start of the infusion of ALN-TTR02. Hydroxyzine or fexofenadine 25 mg PO or cetirizine 10 mg PO may be substituted for any patient who does not tolerate IV diphenhydramine or other IV H1 blocker.

Patients will be started on the above premedication regimen. However, modifications may be made to the premedication regimen after consultation with the medical monitor either due to a patient's inability to tolerate one or more of the premedications or to the occurrence of IRRs unresponsive to slowing of the infusion rate.

- If a patient is having difficulty tolerating the steroid premedication regimen (e.g., patient develops uncontrolled hyperglycemia, altered mental status, or other complication), then lowering of the steroid premedication may be allowed for that patient after consultation with the medical monitor.
- If after consultation with the medical monitor, it is agreed that an individual patient's steroid premedication will be lowered, then the following steps **must be followed**:
 - 1) If the current steroid dosage is 10 mg intravenous dexamethasone or equivalent, then the patient may be lowered in increments no greater than 2.5 mg intravenous dexamethasone or equivalent.
 - 2) After each incremental lowering below 10 mg intravenous dexamethasone or equivalent, the patient must receive three consecutive intravenous doses of patisiran without IRR and continued signs or symptoms of steroid intolerance before further reductions in steroid premedications.
 - 3) The premedication steroid dosage should not be reduced below 5 mg intravenous dexamethasone or equivalent.

Alternatively, if a patient experiences an IRR when 10 mg or less of intravenous dexamethasone or equivalent is used as the steroid premedication, then proceed to Section 5.11.

Further details can be found in the Study Reference Manual.

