6.2.1.3 Post-dose

Patients will remain at the study site for at least 1 hour following completion of dosing for the following assessments:

- Collect blood samples for PK analyses at EOI and 1 hour post-dose for the first dose and every dose up through, and including, the 3 month dosing visit, and then on 6, 9, and 12 month dosing days. Collect blood samples for PK analyses at EOI (+5 minutes) on 15, 18, 21, and 24 month dosing days. If the infusion is stopped and the site is considering restarting the infusion, a PK blood sample will be taken while the infusion is stopped.
- Collect urine for PK at 1 hour post-dose for the first dose and every dose up through, and including, the 3 month dosing visit, and then every 6, 9, 12, 15, 18, 21, and 24 month dosing days.
- Document any AEs, beginning with the initiation of the first infusion.
- Obtain concomitant medications information.

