8.4 Adverse Event Reporting

The Investigator is responsible for reporting all AEs that are observed or reported after the first dose of study drug regardless of their relationship to study drug through the 21 or 56-day Follow-up visit (depending on whether or not the patient plans to enroll into the open-label global extension study).

Any medical condition that is present when a patient is screened and does not deteriorate should not be reported as an AE. However, if it does deteriorate at any time during the study, it should be reported as an AE.

All AEs must be fully recorded in the site's source records and in the patients' CRF, whether or not they are considered to be drug-related. Each AE should be described in

detail: onset time and date, description of event, severity, relationship to investigational product, action taken, and outcome (including time and date of resolution, if applicable).

Adverse events should be followed for the reporting periods defined earlier or until recovery to the normal state has been achieved, whichever occurs first. In the event of a patient not returning to the clinical unit, the outcome of this event will be recorded as lost at follow-up.

For patients who withdraw from the study early, ongoing AEs will be followed until resolution or 28 days from last dose, whichever occurs first.

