8.5 Adverse Event Reporting Period

As stated in [Section 8.4](#), AEs will be assessed for 21 or 56 days following the last dose of study drug (depending on whether or not the patient plans to roll over to the open-label global extension study) or until recovery to the normal state has been achieved, whichever occurs first; all AEs that occur after the start of study drug administration on Day 0 (Baseline) must be reported in detail on the appropriate CRF page and followed to satisfactory resolution, or a period of 21 or 56 days after the last dose of study drug administration (depending on whether or not the patient plans to roll over to the open-label global extension study), whichever is shorter.

Serious AEs will be followed for 21 or 56 days following the last dose of study drug (depending on whether or not the patient plans to roll over to the open-label global extension study), or until satisfactory resolution, or until the SAE is considered by the Investigator to be chronic or the patient is stable, whichever occurs first.

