4.6.2. Adverse Events

All AEs will be coded using the MedDRA coding system and displayed in tables and data listings using system organ class (SOC) and preferred term.

Analyses of AEs will be performed for those events that are considered treatment-emergent, where treatment-emergent is defined per protocol as any AE with onset during or after the administration of study medication through 28 days following the last dose of study drug. In addition, any event that was present at baseline but worsened in intensity or was subsequently considered drug-related by the Investigator through the end of the study will be considered treatment-emergent. Events with a fully or partially missing onset date will be assumed to be treatment emergent unless it can be unequivocally determined (from the partial onset date and/or a partial or complete stop date) that the event occurred prior to the first administration of study medication.

AEs are summarized by the numbers and percentages of subjects reporting a given AE. Therefore, in any tabulation, a subject contributes only once to the count for a given AE (overall, by SOC, by preferred term).

Tabulations by SOC and preferred term will be produced for all AEs, for all AEs related to study medication, for all severe AEs, for all AEs leading to study discontinuation, and for all serious AEs. Separate summary tables will be provided characterizing signs and symptoms of IRRs and AEs related to pre-medications. The incidence and frequency of IRRs over time will also be provided. AEs and serious AEs will be also summarized for Cardiac Subgroup. AEs will be tabulated by preferred term in decreasing order in frequency.

Separate tables will present AE incidence by maximum relationship to study drug and by maximum severity. Subjects who report multiple occurrences of the same AE (preferred term) will be classified according to the most related or most severe occurrence, respectively.

No formal hypothesis-testing analysis of AE incidence will be performed.

All AEs occurring on-study will be listed in subject data listings. A separate listing will be provided for IRRs. Listings will be provided for any AEs caused by pre-medications or any study procedure.

By-subject listings will also be provided for the following: subject deaths, SAEs, and AEs leading to discontinuation.

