4.6.6. Premedication

All patients received premedication in order to reduce the potential of an IRR. The original premedication regimen as outlined below was used at the start of the study. A subset of patients experienced AEs suspected to be related to steroids (eg, flushing) and were transitioned to a modified premedication regimen, with a reduced dose of corticosteroid to mitigate these events, as sanctioned in the protocol. After observing that the subset of patients tolerated the lower corticosteroid dose with no increase in IRRs, the protocol was amended (Global Amendment 1) to transition the rest of the patients to the modified premedication regimen (see below).

The following original premedication regimen was used prior to Global Amendment 1:

- Dexamethasone 8 mg PO or equivalent administered the evening before dosing and 20 mg PO at least 60 minutes prior to the start of the infusion of patisiran;
- Paracetamol 500 mg PO or equivalent administered the evening before dosing and at least 60 minutes prior to the start of the infusion of patisiran;
- H2 blocker PO (e.g., ranitidine 150 mg or famotidine 20 mg or equivalent other H2 blocker dose) administered the evening before dosing and at least 60 minutes prior to start of the infusion of patisiran; and
- H1 blocker PO, 10 mg cetirizine or equivalent (hydroxyzine 25 mg or fexofenadine could be substituted if patient did not tolerate cetirizine) administered the evening before dosing and at least 60 minutes prior to start of the infusion of patisiran.

The following modified premedication regimen was instituted with Global Amendment 1:

- Dexamethasone 10 mg IV or equivalent, administered at least 60 minutes prior to the start of the infusion of patisiran;
- Paracetamol 500 mg PO or equivalent at least 60 minutes prior to the start of the infusion of patisiran;
- H2 blocker IV (e.g., ranitidine 50 mg, famotidine 20 mg, or equivalent other H2 blocker dose) at least 60 minutes prior to the start of the infusion of patisiran; and
- H1 blocker IV, diphenhydramine 50 mg (or equivalent other IV H1 blocker available at the study site) at least 60 minutes prior to the start of the infusion of patisiran. Hydroxyzine

25 mg PO or fexofenadine 30 or 60 mg PO or cetirizine 10 mg PO could be substituted for any patient who did not tolerate IV diphenhydramine or other IV H1 blocker.

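### AE recording starts at the first infusion, so new events from the first premedication or screening procedures are not reliably captured, yet the SAP outputs on such events state no onset limit

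*Protocol*

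**What the plan says.** **Start of collection (Protocol).** Table 1-1, footnote bb: "Adverse events are to be documented beginning with the initiation of the first infusion". Table 1-2, footnote x, gives the same start, and Section 6.2.1.3 repeats it among the post-dose procedures. Section 8.4: "The Investigator is responsible for reporting all AEs that are observed or reported after the first dose of study drug". Section 8.5: "all AEs that occur after the start of study drug administration on Day 0 (Baseline) must be reported in detail". The list of screening activities in Section 6.1 contains no AE item.

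**What comes earlier.** Section 7.6.10 has two skin punch biopsies taken at Screening/Baseline, and Section 6.1 allows screening up to 28 days before the first dose. Section 5.5 sets the steroid premedication as "Intravenous dexamethasone (10 mg) or equivalent, administered at least 60 minutes prior to the start of the infusion of ALN-TTR02", with the other premedications on the same timing. SAP Section 4.6.6 describes the regimen in use at the start of the study as "Dexamethasone 8 mg PO or equivalent administered the evening before dosing and 20 mg PO at least 60 minutes prior", so for those patients premedication began the previous evening.

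**What will be reported (SAP Section 4.6.2).** A separate summary of AEs related to premedications is planned, and "Listings will be provided for any AEs caused by pre-medications or any study procedure". Neither item is limited to events that begin after the first infusion. The treatment-emergent definition in the same section does start at study medication.

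**The concern.** Safety is the primary objective. The biopsies are study procedures, and SAP Section 4.6.6 says the premedication regimen was changed because of AEs suspected to come from the steroid. AEs caused by premedication or by procedures are therefore questions the study means to answer, and the SAP gives them their own outputs. The collection rule leaves an interval in which such an event can begin and end with no clear duty to record it. A reader of the clinical study report would take a listing of all procedure-related AEs to include the baseline biopsies and the first premedication, and would have no sign that it might not.

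**Working it through.** The plan states no figure on this point to reproduce, and SAP Section 3.1 says the sample size was not based on power. The check sets the texts side by side and then sizes the gap.

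**Does any rule cover the interval before the first infusion?**

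- Table 1-1, Table 1-2, Section 6.2.1.3 and Section 8.5: no. All start at the infusion or at study drug administration.
- Section 8.4: partly. Its test is when the event is seen or reported, so a reaction still present during the infusion, or a biopsy complication first mentioned afterwards, could qualify. Section 8.5 tests when the event occurs, so the two sections disagree on such events.
- The deterioration rule in Section 8.4: only for a condition already present at screening. A new event is not covered.
- The medical-history rule (Section 7.1; Table 1-1, footnote c): it sends only AEs of Study ALN-TTR02-002 that are ongoing on Day 0 to medical history.
- Section 8.11: it requires all SAEs to be reported, whatever their relationship to study drug, but gives no start date.
- Concomitant medications are recorded from Screening/Baseline (Section 5.10). Treatment of a biopsy complication could appear in the data with no matching AE.

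What is left is new, non-serious events that begin before the first infusion and are not seen or reported after it. For serious events the duty is unclear.

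**Premedication occasions, 3-weekly schedule.** Dosing runs from Day 0 to Day 735 every 21 days: 735/21 + 1 = 36 per patient. The first is 1/36 = 2.8%. With 28 patients all completing, that is 28 of 28 × 36 = 1,008. On the 4-weekly schedule in Appendix 2 (Day 0 to Day 756) the count is 756/28 + 1 = 28, and 1/28 = 3.6%. For a patient who withdraws early the share is larger, but it is still one occasion.

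**Biopsy sessions.** Screening plus the four clinical activity visits (Days 182, 371, 560 and 749 on the 3-weekly schedule) make 5. One of 5 is 20%, or 28 of 140 sessions. Biopsies: 28 × 2 = 56 at most.

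**Possible number of events.** The documents give no event rate. Let p be an assumed share of patients with a new event in the interval. The expected number is 28p, and the chance of at least one is 1 − (1 − p)^28:

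| Assumed p | Expected events | Chance of at least one |
|---|---|---|
| 1% | 0.28 | 25% |
| 5% | 1.4 | 76% |
| 10% | 2.8 | 95% |

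These are upper limits on what is lost at each p, because Section 8.4 may still bring some of the events in.

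**The case against.** Four arguments stand on the other side.

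- **The start is a deliberate choice.** It is stated in several sections and agrees with the treatment-emergent definition. This holds, and it is why the main AE tables are unaffected.
- **A listing shows what was collected.** SAP Section 4.6.2 does not mention events before the infusion, and its general sentence confines AE analyses to treatment-emergent events, which may also govern the premedication summary. This is a fair reading of the summary. The listing sentence has no such limit, and nothing tells the reader which reading applies.
- **The exposure is small and not new.** Protocol Section 1.6.2.1 says a similar premedication regimen was used in earlier ALN-TTR02 studies. Screening assessments already done in the parent study need not be repeated, so parent-study AE collection may cover some of the interval. The documents do not say whether it does.
- **First doses look to be over.** Protocol Section 1.6.1 reports about 16 months of data as of March 2015, and SAP Section 4.6.6 is written in the past tense. A change to collection would then recover nothing for these patients, and only the SAP statement would help.

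A reader might also infer that a serious event from a screening procedure has no reporting route. The documents do not support that: Section 8.11 asks for every SAE within 24 hours of site awareness and sets no start date, so the duty is unclear rather than absent. Nor do they support the inference that every event before the infusion is missed, given the wording and the deterioration rule of Section 8.4.

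**Conclusion.** The point holds as a minor gap. New events that begin before the first infusion are not reliably captured, Sections 8.4 and 8.5 use different tests, and Section 8.11 is silent on events before Day 0. The SAP outputs on premedication-related and procedure-related AEs would be incomplete for at most one premedication occasion and one of five biopsy sessions per patient. They would not be empty, because later premedications and the four later biopsy sessions are covered.

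The figure of 56 biopsies is an upper limit. It assumes that all 28 patients enrol, that both sites are sampled in each (the lower-leg biopsy depends on clinical status), and that no screening biopsy is carried over from the parent study. It counts biopsies, not lost AEs. How many events are affected cannot be known from the documents.

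**What to change.** In the protocol and eCRF:

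- Record SAEs and AEs related to study procedures from informed consent.
- Record all AEs from the first premedication, including any dose taken the evening before.
- State in Section 8.11 that SAE reporting applies from consent.
- Use one test in Sections 8.4 and 8.5: either when the event occurs, or when it is observed or reported.

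In the SAP, keep the treatment-emergent definition and show the earlier events in a separate pre-infusion listing. For patients already dosed, add a sentence to Section 4.6.2 saying that the premedication summary and the premedication and procedure listings exclude events with onset before the first infusion.

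The cost is a short clarification and a few more AE records at screening. No planned table has to change.

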1 INTRODUCTION

1.1 Background and Rationale

1.1.1 Transthyretin Biology and Impact of Transthyretin Lowering

Transthyretin (TTR), also known as prealbumin, is a tetramer protein produced predominantly by hepatocytes (>95% of TTR is liver-derived), with a small fraction produced in the choroid plexus and retina.¹ The primary physiological role of TTR is to serve as a carrier of retinol (also known as vitamin A); it also plays a minor role as a carrier for thyroxine (T4).

In humans, approximately 15% of T4 circulating in the plasma is bound to TTR; the remainder is predominantly bound to thyroxine-binding globulin (TBG). In the mouse, where TTR plays a greater role as a carrier for T4, the absence of TTR reduces circulating levels of T4 but does not adversely affect the concentration of the hormone in peripheral tissues.^{2,3}

Vitamin A circulates through the plasma primarily bound to retinol binding protein (RBP).¹ The clearance of RBP from the circulation is greatly reduced through its binding to TTR. Because vitamin A is lipid-soluble, it can diffuse across the membranes of cells and thus, most tissues receive adequate levels of vitamin A obtained normally from the diet without its being bound to RBP. Studies performed in TTR-knockout mice have demonstrated that in the absence of TTR, circulating levels of both RBP and vitamin A are dramatically reduced (e.g., 5% of vitamin A seen in wild type [WT] mice); however, the concentration of vitamin A in the tissues is comparable with that seen in WT mice.^{4,5} In addition, the TTR-knockout mice did not demonstrate any signs of vitamin A deficiency. In humans, individuals with mutations in the RBP gene leading to complete loss of circulating RBP and very low concentrations of circulating vitamin A have not shown any significant signs of vitamin A deficiency other than modest retinal dystrophy and decrease in night vision.⁶ This confirmed the finding in mice that vitamin A uptake by most tissues continues in the absence of RBP. In women with breast cancer treated for an average of at least 30 months with the retinoid fenretinide, which causes a 75% reduction in circulating vitamin A levels, there were no reports of night blindness or any other signs of vitamin A deficiency, and only subtle changes in retinal function were seen on electroretinograms in women older than 50 years of age who were on fenretinide for 30 months or longer.^{7,8} The safety of lowering vitamin A through TTR suppression has now been further confirmed by the absence of any vitamin A deficiency-related AEs in non-human primates treated with ALN-TTR02 at doses up to 2 mg/kg every 3 weeks for 9 months, and in both healthy volunteers and familial amyloidotic polyneuropathy (FAP) patients treated with ALN-TTR02 who experienced substantial lowering of both TTR and vitamin A (see [Section 1.3](#)).

